## 2. Study Design Overview

This study is a pilot randomized controlled trial (pilot RCT) using a longitudinal cohort design among young men who have sex with men (YMSM) aged 15–29 years, with a total of 100 participants equally allocated into two groups:

- STOS intervention group (n = 50)
- Control group (n = 50)

Participants will be followed for a period of 12 months, with data collection conducted at three times: baseline, 6 months, and 12 months of follow-up.

### 2.1 Data Collection and Sources

Data will be obtained through an online, self-completed survey administered via the Qualtrics platform, which participants can access on mobile phones or tablets. To protect confidentiality, the survey will not gather any personal identifiers. Participants will instead log in using the same chosen nickname or pseudonym and their approved contact method, enabling the research team to reliably match their responses across multiple survey waves without compromising anonymity.

### 2.2 Retention and Follow-up

To maintain strong participant retention throughout the study, the research team will employ ongoing engagement activities delivered through digital communication channels and peer-supported community networks.

### 3. Study Objectives and Endpoints

#### 3.1 Primary Objective

To evaluate the effectiveness of the STOS intervention in increasing access to and uptake of HIV testing among young men who have sex with men (YMSM).

#### 3.2 Secondary Objectives

- To evaluate the effect of the intervention on reducing the incidence of HIV infection.
- To evaluate the effect of the intervention on reducing sexual risk behaviors (e.g., condomless anal intercourse with male partners).
- To evaluate the effect of the intervention on reducing health-related risk behaviors, including mental health problems (depression and suicidal risk) and substance use.

#### 3.3 Primary Outcome

- **HIV testing uptake:**

Proportion of participants who report having tested for HIV at least once within a 6-month period, based on STOS testing records and self-reported survey data.

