## 2.1 Procedures

### 2.1.1 Recruitment and Enrollment

Participant recruitment will be conducted over a one-year period, using a combination of online and offline outreach strategies to reach the target population of young men who have sex with men (YMSM) in Ho Chi Minh City.

For the online cross-sectional survey, recruitment will primarily be conducted through online platforms, including Google advertisements, Facebook, the CARMAH fan page, CARMAH networks, other MSM community networks, and youth networks in Ho Chi Minh City (such as university and high school students). To encourage participation, each respondent will receive a mobile top-up e-voucher valued at 50,000 VND (approximately 2 USD), delivered via SMS.

Individuals interested in participating will complete an online eligibility screening form. Those who meet the inclusion criteria will receive detailed study information and proceed with the initial electronic consent (e-consent). After completing the survey, if an individual is found to be HIV-positive, they will not be invited to participate in the pilot study.

For the pilot study, a total of 100 Vietnamese YMSM will be recruited and followed for 12 months. Participants will be randomly assigned into two groups of 50 each:

- The intervention group, which will receive the HIV self-testing with online supervision (STOS) intervention; and
- The control group, which will refer to the standard of care, consisting of a voucher for venue-based HIV testing.

The STOS program begins when a counsellor contacts eligible participants via the Zalo communication platform. After confirming eligibility, the counsellor obtains verbal informed consent and schedules an appointment for the HIV self-testing with online supervision (STOS) session.

Once the appointment is confirmed, HIV self-testing kits are delivered to participants through Be Delivery service. Before the testing session, participants receive a link to an instructional YouTube video developed by CARMAH and Mahidol University, which demonstrates the correct procedure for performing the HIV self-test.

During the scheduled session, the counsellor provides pre-test counselling and real-time supervision via video conferencing as participants perform the self-test. This process ensures proper use of the test kit, supports accurate interpretation of results, and maintains participant confidentiality throughout the HIV self-testing process.

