### 2.1.2 Data Collection

Data collection will occur at three time points: at baseline and again at 6 and 12 months of follow-up. During each assessment, participants will complete self-administered questionnaires on tablets or smartphones via the Qualtrics platform. For individuals assigned to the STOS group, HIV self-testing outcomes will be documented by a trained counselor and stored in an encrypted file with restricted access. Only the Principal Investigator (PI) and the Study Statistician will be authorized to view these data to maintain strict confidentiality.

All study data will be housed on secure institutional servers in encrypted, password-protected formats to ensure robust data security.

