#### 2.4.2 Primary and Secondary Outcome Analyses

To evaluate the effects of the STOS intervention, two groups will be compared: the STOS group, who receive an HIV self-testing kit and complete the online questionnaires, and the control group, who complete the questionnaires only. The primary outcomes are the rate of HIV testing uptake and the rate of new HIV infections during the study period. The secondary outcomes include changes in sexual behaviors, mental health, and other psychosocial indicators over time. To assess the effects of the intervention across time points, Generalized Estimating Equations (GEE) models will be applied, using a log link function for rate outcomes and an identity link function for continuous outcomes. The models will include variables for study arm (STOS vs. control), time (follow-up round), and their interaction term (arm  $\times$  time) to estimate longitudinal intervention effects. Robust standard errors will be used to account for within-subject correlation due to repeated measures. The results will be presented as Rate Ratios (RRs or Incidence Rate Ratios, IRRs) with 95% confidence intervals (CIs) and p-values to indicate the magnitude and statistical significance of the observed effects.

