#### 3.4 Secondary Outcomes

- **HIV incidence:**

Number of new HIV infections per 100 person-years, based on STOS testing results and self-reported data during follow-up.

- **Sexual risk behavior:**

Proportion of participants reporting condomless anal intercourse with male partners during the past 6 months, measured through self-reported survey data.

- **Health-related risk behaviors (mental health and substance use):**

Proportion of participants reporting mental health problems (e.g., depressive symptoms, suicidal risk) and frequency of substance use during the past 6 months, based on self-reported survey data.

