## 5.2 Data Cleaning and Preparation

After exporting the data from Qualtrics, the research team will conduct structured cleaning procedures using STATA command scripts to ensure accuracy and consistency. Key tasks will include identifying outliers, detecting logically inconsistent answers, checking the correctness of skip patterns, and verifying that numerical variables fall within acceptable ranges. Variables that depend on previous responses will also be reviewed to confirm internal coherence.

For the preparation of the analytic dataset, information from two sources will be combined: (1) the self-administered online questionnaires collected through Qualtrics, and (2) HIV self-testing outcomes obtained from participants in the STOS intervention group. These datasets will be harmonized before merging. To ensure accurate linkage across time points, participants will be asked to provide the same nickname or pseudonym during every round of data collection.

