## 6.2 Primary and Secondary Outcome Analyses

Generalized Estimating Equations (GEE) with appropriate link functions (e.g., logit for binary outcomes, identity for continuous variables) will be applied to assess intervention effects

over time. Each model will include study arm, follow-up time, and an interaction term to estimate differential changes between groups. Robust standard errors will be used to account for correlations within individuals. Person-time will also be calculated, and rate ratios with 95% confidence intervals will be reported.

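### The primary testing-uptake outcome draws on counsellor records that exist only in the STOS arm, with no rule for combining them with self-report and no planned comparison of the arms on one source

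*Combined protocol and SAP*

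**What the plan says.** SAP 3.3 names one primary outcome, the proportion tested "at least once within a 6-month period, based on STOS testing records and self-reported survey data". The sentence opens by counting participants who report a test, but then names records as a basis alongside the survey.

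Only one arm has such records. Protocol 2.1.2: "For individuals assigned to the STOS group, HIV self-testing outcomes will be documented by a trained counselor". SAP 5.2 builds the analysis dataset from two sources: the questionnaires, and "HIV self-testing outcomes obtained from participants in the STOS intervention group". Controls receive standard of care, "consisting of a voucher for venue-based HIV testing" (protocol 2.1.1), but neither voucher redemption nor a venue result is listed as data. Protocol 2.4.2 describes "the control group, who complete the questionnaires only". That phrase concerns what participants do and leaves out the voucher, so SAP 5.2 is the firmer evidence on data sources.

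On analysis, SAP 6.2 plans GEE: "Each model will include study arm, follow-up time, and an interaction term to estimate differential changes between groups". The sensitivity analyses in SAP 7 vary the model specification, the link, and GEE against mixed models. Those in SAP 5.1 concern missing data. Neither varies the data source.

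HIV incidence, secondary in SAP 3.4 but primary in protocol 2.4.2, is likewise "based on STOS testing results and self-reported data during follow-up".

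**The concern.** A STOS participant who was tested but does not say so in the survey may be recovered from the counsellor's record. A control in the same position cannot be. Part of any difference in measured uptake could therefore come from having a second source in one arm.

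The arm × time model does not remove this. Protocol 2.1.1 states: "The STOS program begins when a counsellor contacts eligible participants via the Zalo communication platform". Baseline testing history is therefore self-reported in both arms, and the extra source enters one arm only at follow-up, which is the contrast that the interaction estimates. Changing the link or moving to a mixed model would analyse the same unequal outcome.

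What is at stake is mainly the size of the estimated effect. SAP 3.1 sets an effectiveness objective, and protocol 5 foresees exploring scale-up and possibly policy briefs.

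**Working it through.** The plan gives no assumed uptake, effect size or reporting accuracy, so there is no figure to reproduce. What follows is an illustration.

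**Inputs**
- From the documents: 50 per arm (protocol 2); retention expected above 80% (protocol 2.1.3); 76.5% never tested (protocol 1.2), so 100 − 76.5 = 23.5% ever tested. The last is used only as a low value for uptake, since ever tested is not the same quantity as tested within 6 months.
- Assumed: true uptake u, equal in both arms; self-report sensitivity Se = 0.90 in both arms; no false reports; recorded share of STOS-arm tests q = 0.80; recording independent of reporting.

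**Either source counts**
- Control: u × Se
- STOS: u × [1 − (1 − Se)(1 − q)]
- Difference: u × q × (1 − Se), never below zero. An equal false-report rate among the untested in both arms cancels.

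| True uptake | STOS | Control | Difference |
|---|---|---|---|
| 23.5% | 0.235 × 0.98 = 23.0% | 0.235 × 0.90 = 21.2% | 0.235 × 0.8 × 0.1 = +1.9 points |
| 60% | 0.60 × 0.98 = 58.8% | 0.60 × 0.90 = 54.0% | 0.60 × 0.8 × 0.1 = +4.8 points |

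At 60% the spurious odds ratio is (0.588/0.412)/(0.540/0.460) = 1.22.

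Range over Se 80–95% and q 60–100%:
- Uptake 23.5%: 0.235 × 0.6 × 0.05 = +0.7 to 0.235 × 1 × 0.2 = +4.7 points.
- Uptake 50–70%: 0.5 × 0.6 × 0.05 = +1.5 to 0.7 × 1 × 0.2 = +14 points.
- Se = 1: zero throughout.

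**Other rules, uptake 60%**
- Both sources required in STOS: 0.60 × 0.8 × 0.9 = 43.2% against 54.0%, −10.8 points.
- Record replaces self-report in STOS: 0.60 × 0.8 = 48.0% against 54.0%, −6.0 points.

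The sign therefore depends on a rule that the SAP does not state.

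**False-positive rate**
The planned model was simulated with no true difference: logit GEE, arm × time at 12 months, 50 per arm, 60% follow-up uptake, 80% response, and an assumed baseline of 23.5%. In 1,500 runs it rejected 6.1% of the time on the same questionnaire item and 5.1% with either source. A separate 600 runs gave 4.8% and 7.2% (Monte Carlo standard error about 1 point). No clear inflation appears at these inputs. More extreme inputs would do more: a single-visit z-test at 80% uptake, Se 80% and every STOS test recorded rejects 42.8%.

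**With a real effect, assumed 80% v 50%**

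| Measure | STOS | Control | Difference | Odds ratio |
|---|---|---|---|---|
| Truth | 80.0% | 50.0% | 30.0 | 4.00 |
| Same item | 0.8 × 0.9 = 72.0% | 0.5 × 0.9 = 45.0% | 27.0 | (0.72/0.28)/(0.45/0.55) = 3.14 |
| Either source | 0.8 × 0.98 = 78.4% | 45.0% | 33.4 | (0.784/0.216)/(0.45/0.55) = 4.44 |

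The two measures miss in opposite directions.

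**Imputation**
At 60% uptake, 0.6 × 0.8 = 48% of the STOS arm have a record. Of the other 52%, 0.6 × 0.2 × 0.9 = 10.8% of the arm would report a test, a share of 0.108/0.52 = 0.2077. Imputing within record status gives 0.48 + 0.52 × 0.2077 = 58.8%, the full-response value.

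**The case against.** **Direction.** A reader might infer that the plan favours STOS by definition. The documents do not support this. SAP 3.3 counts people who report a test, so records may only corroborate, and no combination rule is written. The direction towards STOS is conditional on the either-source reading and on similar reporting error in the arms. If 0.048/0.40 = 12% of untested controls, and no untested STOS participants, falsely reported a test, the +4.8 points would vanish. If recorded tests are also better remembered, the gap shrinks, though it does not reverse.

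**Larger figures.** Suppose records fill in missed surveys at 80% response and other non-responders are dropped. STOS becomes (0.8 × 0.588 + 0.2 × 0.48)/(0.8 + 0.2 × 0.48) = 63.2%, a gap of about 9 points. The plan does not specify that handling. SAP 5.1 allows complete-case analysis only when little is missing, 80% is the floor of expected retention, and nothing says that imputation would ignore the record.

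**Self-report as primary.** A reader might infer that the outcome should be self-report alone. That does not follow. At 80% v 50% the either-source odds ratio is the closer to the truth; at 70% v 50% the same-item one is slightly closer (2.08 and 2.67 against 2.33). It is a trade-off.

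**Scale.** This is a pilot, and feasibility and acceptability form its Aim 3. At 50 per arm, +4.8 points is about half a standard error: 0.048/√(2 × 0.564 × 0.436/50) = 0.48. That limits the harm.

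What stands is that the sources are unequal, the rule is missing, and no listed analysis shows how much the extra source contributes. SAP 7 is worded openly, but an unlisted analysis is not prespecified.

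**Conclusion.** The point holds as a gap in outcome definition that is cheap to close. That ascertainment is unequal is clear from the documents. The direction is conditional: zero or towards STOS if either source counts and reporting error is equal, and possibly against STOS under the other rules. The size is uncertain because uptake, sensitivity and recorded share are all assumed; +1.9 to +4.8 points is an illustration, not an estimate of this trial's bias. At those inputs the concern is the effect estimate, not the false-positive rate.

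HIV incidence has the same unequal sources, but there extra detection would raise the observed incidence in STOS and so work against it. The direction for uptake should not be carried over.

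**What to change.** - **SAP 3.3:** state how records and self-report combine, including what happens when they disagree and how a STOS survey non-responder with a record is classified.
- **SAP 7:** prespecify a comparison of the arms on the same 6- and 12-month questionnaire item, with records neither overwriting nor filling in answers. Report it beside the record-inclusive result.
- **SAP 5.1:** if outcomes are imputed, include the record in the imputation model for the record-inclusive analysis.
- **SAP 3.4:** report the same-source comparison for HIV incidence too.

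Which version is primary is the sponsor's choice.

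The cost is SAP wording and one extra analysis per outcome, from data already planned in both arms. The same-item result has its own weaknesses. It relies on recall, it is biased if reporting or survey response differs by arm, and equal under-reporting shrinks a real risk difference and odds ratio. That is why both results should be shown.

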#### 3.4 Secondary Outcomes

- **HIV incidence:**

Number of new HIV infections per 100 person-years, based on STOS testing results and self-reported data during follow-up.

- **Sexual risk behavior:**

Proportion of participants reporting condomless anal intercourse with male partners during the past 6 months, measured through self-reported survey data.

- **Health-related risk behaviors (mental health and substance use):**

Proportion of participants reporting mental health problems (e.g., depressive symptoms, suicidal risk) and frequency of substance use during the past 6 months, based on self-reported survey data.

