## 2.3 Consent

### 2.3.1 Consent Procedures

All participants will provide informed consent by clicking "accept button" at the time they begin the online survey. For participants under 18 years of age, a waiver of parental consent will be obtained from the ethics committee to protect them from the potential risk of unintentional

disclosure of their sexual orientation or HIV status. Before joining the study, participants will receive a study information sheet explaining the research objectives and procedures. This document will appear immediately before the consent question in the online survey, allowing participants to review the study details before providing consent. After completing the survey, participants who are interested in joining the STOS intervention will be introduced to additional information, as follows: Participants will be informed that the study involves an online HIV self-testing intervention and that they may be randomly assigned to one of two testing approaches.

The first approach involves receiving an HIV home self-testing kit, with real-time guidance and support from trained staff via video calls and instructional videos. The second approach involves receiving information about free HIV testing services available at public hospitals, where participants can go for testing independently. If selected for participation, study staff will contact participants using the contact information provided to explain further details and confirm their willingness to take part. For those who are randomly assigned to the STOS group, multiple formats will be used to ensure a full understanding of study procedures. These include printed materials, instructional videos (e.g., how to perform HIV self-testing), and verbal explanations provided by trained counsellor. Participants will be encouraged to ask questions about any aspect of the study, including the survey process, HIV self-testing procedures, and their right to withdraw from the study at any time without penalty or loss of benefits. Informed consent will be obtained only after participants demonstrate clear understanding and express their willingness to participate voluntarily. At each follow-up round, field staff will reassess participants' understanding and verbally reconfirm consent before administering questionnaires or conducting STOS sessions, to ensure that participants remain fully informed and voluntarily engaged throughout the longitudinal study

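### HIV infections are found by recorded tests plus self-report in STOS but by unverified self-report alone in controls, so the planned incidence rate ratio cannot show an effect on acquisition

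*Combined protocol and SAP*

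**What the plan says.** SAP 3.4 defines the incidence outcome as "Number of new HIV infections per 100 person-years, based on STOS testing results and self-reported data during follow-up". The test-based part of that definition is available in one arm only. Protocol 2.1.2 states: "For individuals assigned to the STOS group, HIV self-testing outcomes will be documented by a trained counselor". SAP 5.2 builds the analysis file from two sources, the questionnaires and "HIV self-testing outcomes obtained from participants in the STOS intervention group".

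The control arm is described in three ways. Protocol 2.1.1 has "The control group, which will refer to the standard of care, consisting of a voucher for venue-based HIV testing". The consent text in protocol 2.3.1 has "The second approach involves receiving information about free HIV testing services available at public hospitals, where participants can go for testing independently". Protocol 2.4.2 has "the control group, who complete the questionnaires only". None of these adds a control-arm test record to the data.

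On HIV status at entry, protocol 2.1.1 says that after the online survey "if an individual is found to be HIV-positive, they will not be invited to participate in the pilot study". The eligibility lists in protocol 2.2 contain no HIV-status criterion, and no test before randomisation is described.

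On purpose and rank, SAP 3.2 sets a secondary objective of evaluating a reduction in HIV incidence, and SAP 6.2 plans person-time and rate ratios with 95% confidence intervals. Protocol 2.4.2 ranks the outcome higher: "The primary outcomes are the rate of HIV testing uptake and the rate of new HIV infections during the study period". It adds rate ratios and p-values.

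**The concern.** SAP 3.1 gives the aim of STOS as raising HIV testing. Testing is also how infections come to light. If STOS succeeds on its main aim, more of the infections in that arm will be found, whether or not any were prevented. A control with an undiagnosed infection answers the questionnaire truthfully and is counted as event-free.

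The ratio therefore mixes a change in detection with any change in acquisition, and the plan has no means of separating them. The missing case definition adds to this. A positive result at a man's first study test may be an infection that he already had at enrolment, and the plan does not say how to classify it. At stake is a result that the protocol calls primary and that would be read as evidence on whether STOS prevents HIV.

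**Working it through.** **Inputs from the documents.** 50 men per arm followed for 12 months (protocol section 2). Incidence of 5.8% in young MSM in Hanoi and prevalence of 17% in MSM in Ho Chi Minh City (protocol 1.1).

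**Assumptions.** The 5.8% is read as 5.8 per 100 person-years and carried over to Ho Chi Minh City. Detection shares are not in the documents; the grid is dS = 0.8 or 0.9 in STOS and dC = 0.4 or 0.6 in controls. Person-time is equal in the two arms. There is no planned figure to reproduce: the sample size of 100 comes with no power, effect size or event target.

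**1. Do the planned safeguards help?** SAP 5.1 deals with missing values (imputation or likelihood methods under missing at random, with pattern-mixture sensitivity analyses). An undiagnosed control who completes the survey has no missing value; he is recorded as uninfected. SAP 7 varies the model and the link. Neither changes how cases are found.

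**2. Size of the detection effect.** Let u be the share of enrolled men with undiagnosed infection at entry and i the share newly infected. If detected positives count as new, and old and new infections are detected equally within an arm, then with no true effect:

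observed ratio = dS(u + i) / [dC(u + i)] = dS/dC

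With nobody infected at entry (u = 0), a true halving appears as 0.5 × dS/dC.

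| dS | dC | No true effect | True halving, u = 0 |
|---|---|---|---|
| 0.8 | 0.6 | 1.33 | 0.67 |
| 0.9 | 0.6 | 1.50 | 0.75 |
| 0.8 | 0.4 | 2.00 | 1.00 |
| 0.9 | 0.4 | 2.25 | 1.12 |

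**3. Can the direction change?** Let p = 0.17, let a be the share of infected men already aware and screened out (0.2, 0.5 or 0.8, assumed), and let r = 1 − exp(−0.058) = 0.0564. Then u = p(1 − a)/(1 − pa) and i = (1 − u)r. At a = 0.2, u = 0.1408 and i = 0.0484. At a = 0.8, u = 0.0394 and i = 0.0541. Let d2 be the detection of new infections in STOS.

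- *New infections found less often than old ones in STOS (d2 = 0.4).* Null ratio = (dS·u + d2·i) / [dC(u + i)]. Lowest: (0.8 × 0.0394 + 0.4 × 0.0541) / (0.6 × 0.0935) = 0.95. Highest: (0.9 × 0.1408 + 0.4 × 0.0484) / (0.4 × 0.1892) = 1.93.
- *First-test positives excluded in STOS only.* Null ratio = d2·i / [dC(u + i)]. With d2 = 0.8 to 0.9 it runs from 0.8 × 0.0484 / (0.6 × 0.1892) = 0.34 to 0.9 × 0.0541 / (0.4 × 0.0935) = 1.30. With d2 = 0.4 it is 0.17 to 0.58.

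With no true effect, the ratio can therefore fall on either side of 1, depending on rules that the plan leaves open.

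**4. Precision, apart from bias.** Expected infections per arm with complete follow-up = 50 × 1 × 0.058 = 2.9; under a true halving STOS would have 1.45. With equal and complete testing, an exact conditional binomial test at two-sided 0.05 (assumed) on Poisson means of 1.45 and 2.9 has power 2.1%. The chance that at least one arm has no case is 1 − (1 − e^−1.45)(1 − e^−2.9) = 28%.

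**The case against.** The best defence has four parts.

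*Control self-report can carry real results.* A control may use the voucher or a public hospital and report the outcome. This stands: control detection is not zero, and results are collected in that sense. What is absent is verification, and anything that makes detection equal across arms.

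*The detection shares are assumed.* This also stands, so the ranges illustrate the problem and do not predict its size. The conclusion needs only that detection differs by arm.

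*The plan does not say that every first positive is new.* SAP 3.4 speaks of new infections during follow-up, and protocol 2.1.1 keeps out people found positive. A reader might infer that prevalent cases will be counted as incident, or combine the 17% prevalence with the 76.5% never tested (protocol 1.2) and conclude that most detected infections will be old. The documents do not support either inference: they are silent on first-test positives, and both figures describe MSM in general, not volunteers aged 16 to 29. The fault is the missing rule. Even with nobody infected at entry, unequal detection in follow-up remains.

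*This is a pilot, and the SAP ranks incidence second.* Low power alone is no fault in a pilot. But SAP 3.2 sets an effectiveness objective, and protocol 2.4.2 makes incidence a primary outcome with p-values.

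**Conclusion.** The concern holds. Recorded tests feed the incidence outcome in one arm only, the intervention acts on testing itself, and the plan still presents the between-arm ratio as an effect on incidence. As written, that ratio cannot be interpreted as an effect on HIV acquisition.

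The size is illustrative. The null ratio of 1.33 to 2.25 rests on 80-90% against 40-60% detection, on detected positives being counted as new, and on old and new infections being equally detectable within an arm. It does not hold at every prevalence once that last condition fails.

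A reader might go further and infer that the trial will make STOS look harmful. That does not follow. The direction depends on case rules that are not written, and counts this small would establish nothing: 6 detected cases against 3 (rounded from 5.8 and 2.9, using 17% prevalence, half of infected men aware, and 80% against 40% detection) gives an exact 95% interval for the ratio of 0.43 to 12.4. The rank conflict between protocol 2.4.2 and SAP 3.4 makes the matter more pressing but is not its source.

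**What to change.** Make three changes together.

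1. **Drop the effectiveness comparison.** In protocol 2.4.2 and SAP 3.2 and 6.2, remove the between-arm rate ratio and p-value for HIV incidence and restate the objective as descriptive. Report newly diagnosed HIV by arm and by source (recorded test or self-report) in the ITT population with exact confidence intervals. State that detection differs by arm and that no effect on acquisition can be inferred.
2. **Define an incident case in SAP 3.4.** Label a positive first study test as newly diagnosed with timing unknown: not incident, and not automatically prevalent, since a first test at month 6 or 12 could reflect infection after enrolment. Count a case as incident only after a documented negative on-study test, with person-time starting at that negative. Label any STOS-only incidence estimate exploratory and non-ITT, and omit it if too few men test twice.
3. **Reconcile the ranking.** Make protocol 2.4.2 agree with SAP 3.3 and 3.4, with HIV testing uptake as the sole primary outcome. SAP 3.3 draws uptake from the same unequal sources, so base the between-arm comparison on the survey self-report item collected in both arms and report STOS records as supplementary.

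The same documented entry and exit HIV test in both arms would remove the detection bias, but power for a halving would stay near 2%, so it would not rescue a confirmatory comparison at this size.

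**Cost.** Changes 1 and 3 need no new data. Change 2 needs dated STOS results; the documents do not fix the number or timing of sessions, so STOS incidence may prove inestimable. The trial gives up an incidence-reduction claim that it could not support, and both documents must be amended through the usual approvals.
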